## Data collection

Pseudonymized patient data is reported from participating study sites through a secure online platform (Redcap™) on 1) admission, 2) on the day of each indirect calorimetry, and 3) on ICU discharge or death.

Participating centers are responsible for creating and maintaining a secure code key linking the study number attributed to a patient with a patient ID, to be stored in a secure location at the study site.

On admission:

- Admission date
- Admission diagnosis (ICD-10)
- Surgery prior to admission (YES/NO), elective or emergent
- ICU source of admission (Emergency department, ward, operating theatre, other ICU).
  - If ward or operating theatre → days in hospital before ICU admission.
  - If other ICU → days in previous ICU before admission.
- Outcome prediction score (SAPS 3, APACHE III/IV, MPM, etc.) and risk of death on admission (%)
- Demographic and anthropometric data:
  - Sex (male/female)
  - Age (years)
  - Actual body weight (kg)
  - Height (cm)
- Chronic comorbidities registered in electronic health records (YES/NO):
  - Hypertension
  - Ischemic heart disease
  - Heart failure

- Diabetes mellitus
- COPD
- Chronic kidney disease
- End-stage renal disease
- Liver cirrhosis
- Active cancer (not in complete remission)
- Haematological malignancy
- Solid organ transplant

On the day of each indirect calorimetry:

- REE (kcal/24 h), RQ,  $\text{VO}_2$  (ml/min),  $\text{VCO}_2$  (ml/min) and date of investigation
- Invasive mechanical ventilation (YES/NO) or renal replacement therapy (YES/NO)
- If YES to invasive mechanical ventilation:
  - fraction of inspired oxygen
  - positive end-expiratory pressure (cm  $\text{H}_2\text{O}$ )
- Sequential organ failure assessment (SOFA) score
- Fever ( $\geq 38.5^\circ\text{C}$ ) within 2 hours of measurement (YES/NO/MISSING)
- Results of daily blood tests if available from routine testing:
  - P-CRP (mg/L)
  - P-albumin (g/L)
  - P-urea (mmol/L)
  - P-creatinine ( $\mu\text{mol/L}$ )
  - Haemoglobin (g/L)
- Infusions of vasoactive medications (YES/NO, if YES → name of medication(s))
- Infusions of sedatives or analgesics (YES/NO, if YES → name of medication(s), if propofol → infusion rate at time of measurement)
- Infusions of parenteral and/or enteral nutrition (YES/NO, if YES → formulation and rate at time of measurement)
- Richmond Agitation-Sedation Scale (RASS) score on day of measurement

On discharge:

- Discharge date
- Survival status (ALIVE/DEAD)

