Generalised linear mixed regression models will be used to study the association between primary (REE) as well as secondary outcomes (RQ,  $\text{VO}_2$ ,  $\text{VCO}_2$ ) and explanatory variables of interest. Explanatory variables will include a group of potentially relevant variables (days in ICU on measurement, age  $>/<$  60 years, sex, airway pressure (PEEP),  $\text{FiO}_2$ , vasopressor therapy (yes/no), fever (body temperature  $\geq 38.5^\circ\text{C}$  at time of measurement), calories administered at time of measurement, Richmond Agitation-Sedation Scale (RASS), degree of inflammation (plasma CRP), renal replacement therapy (yes/no), body weight, diagnostic group (medical, surgical, presence/absence of sepsis)). Further variable selection will be conducted in a data-driven way, either backward or forward selection, as appropriate. For each outcome, the link function and model family will be chosen based on the visual inspection of their distribution and model fit diagnostics such as residual plots. Patient and study site will be included as random effects allowing for a random intercept for each. Random slopes over time will be included in the model if their respective estimated coefficients are statistically significant and if the model fit in terms of Akaike's information criterion (AIC) is improved compared to the random intercept model. Possible correlations between the random effects will be modelled using an unstructured covariance matrix unless the AIC suggests a different covariance structure for best describing the random variation in the data. Any additional explanatory variables will be treated as fixed effects. For each additional explanatory variable, we will investigate two research questions. First, we want to explore possible associations with each outcome variable. Second, we want to study how well the explanatory variables taken together explain the variation in each outcome variable. The best final adjusted models will be selected based on the AIC. Results will be reported as (exponentiated) regression coefficients and 95% confidence intervals. If a non-linear relationship between any outcome and any explanatory variable is suspected, using restricted cubic splines will be explored.

---

 Classified as Sepsis-3 och primary diagnosis of sepsis. Sepsis-3 coding is not available in the Australian cohort. A sensitivity analysis including or excluding the primary diagnosis of sepsis will be performed.

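### The SAP names no time term or contrast for the primary test of change in REE, and its one stated model-building procedure would give a covariate-conditional answer if used for it

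*Combined protocol and SAP*

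**What the plan says.** In the protocol, the Outcomes section defines the primary outcome as change over time in REE, in kcal per kg adjusted body weight per 24 hours, among patients whose ICU stay exceeds 10 days. The Hypothesis section expresses it as a change in mean between three phases: days 1-3, days 4-10 and after day 10. The Statistics section names a generalised linear mixed-effects model and defers the detail to the SAP.

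The SAP (updated 2025-04-08) fixes the model class and random intercepts for patient and site. It ties the 0.05 level to the primary outcome and treats the remaining outcomes as explorative. On building the model it says:

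- "Explanatory variables will include a group of potentially relevant variables (days in ICU on measurement, age". The list goes on to sex, body weight and diagnostic group, and to PEEP, FiO2, vasopressors, fever, calories, RASS, CRP and renal replacement therapy.
- "Further variable selection will be conducted in a data-driven way, either backward or forward selection, as appropriate"
- "For each additional explanatory variable, we will investigate two research questions": association with each outcome, and joint explanation of its variation.
- "The best final adjusted models will be selected based on the AIC"
- "For each outcome, the link function and model family will be chosen based on the visual inspection of their distribution", together with fit diagnostics.
- "Results will be reported as (exponentiated) regression coefficients and 95% confidence intervals"

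**The concern.** One test in this study has a set significance level of its own, and the reader cannot tell from the SAP what that test is. The Hypothesis section asks whether mean REE changes across the ICU stay, whatever the reason. A day coefficient adjusted for same-day CRP, fever, sedation and vasopressors asks whether REE changes with day among measurements alike on those variables. If recovery from inflammation is part of why REE changes, the second question removes part of the answer to the first.

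Two further matters follow. A coefficient from a model chosen by searching over covariates has a confidence interval and p-value that ignore the search. And because the link is chosen from the data and coefficients may be exponentiated, it is not settled whether the primary result is a difference in kcal/kg or a ratio.

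**Working it through.** The plan gives no effect size, SD or power for this test, so there is no figure to reproduce. Its target of at least 200 long-stay patients is a recruitment goal.

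**Step 1. What a primary test needs, and where it is fixed.**

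- Outcome unit and population: fixed in Outcomes. The SAP says only REE, lists body weight as an explanatory variable, and does not restate the population.
- Form of time: three phases in Hypothesis; days in ICU in the SAP, with splines if non-linearity is suspected. Not fixed.
- Coefficient, joint test or contrast at 0.05: not named.
- Time kept whatever the selection does: not stated.
- Family, link and reporting scale: decided from the data.
- Random intercepts: fixed.

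**Step 2. The two estimands.** Let REE/kg depend on day with direct effect b per 10 days, and on a same-day covariate with effect c per SD. Let the covariate move d SD per 10 days. Then overall change = b + c × d, while the covariate-adjusted day coefficient estimates b. They agree only when c × d = 0.

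Assumed inputs: 200 patients measured on days 2, 5, 9, 12 and 16; between-patient SD 3.5 and within-patient SD 2.5 kcal/kg; b = 1.0; d = -0.8; 2000 runs.

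- c = 0.5: overall 1.0 - 0.4 = 0.6, adjusted 1.0. The linear time test rejects in 95% of runs unadjusted and 100% adjusted.
- c = 1.0: overall 1.0 - 0.8 = 0.2, adjusted 1.0. Rejection 20% and 100%.
- c = 1.25: overall 1.0 - 1.0 = 0.0, adjusted 1.0. Rejection 5% and 100%.

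A second set of assumed inputs adds the selection step: 200 patients with 5 measurements each, patient SD 3, residual SD 2.5, site SD 1 over 10 sites, patient slope SD 1 kcal/kg per 10 days, and 12 candidate covariates of which 3 drift with day. Day is forced in, backward AIC is applied to the rest, and there are 300 runs per setting. The overall change is held at 1.0, so the expected adjusted value is 1.0 × (1 - share carried by covariates):

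- share 0%: expected 1.00, simulated 0.99
- share 30%: expected 0.70, simulated 0.73
- share 50%: expected 0.50, simulated 0.50
- share -50%: expected 1.50, simulated 1.49

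The time-only model averages 0.98 to 0.99 throughout.

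**Step 3. Selection alone.** On the second set of inputs with no time effect (1000 runs), rejection at nominal 0.05 and its Monte Carlo 95% interval, p ± 1.96 × √(p(1-p)/1000), are:

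- covariate drift 0 SD per 10 days: 4.8% (3.5 to 6.1)
- drift 0.5 SD: 6.2% (4.7 to 7.7)
- drift 1.0 SD: 9.0% (7.2 to 10.8)

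Only the last interval excludes 5%. A prespecified 2-df phase test gave 4.6%, but that test has no covariates, so the comparison is not like for like.

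**Step 4. Room left open.** On the first set of inputs, with no time effect and no covariate effect, six readings were tried: linear day, three-phase joint test, late versus early, spline, and linear and phase with adjustment. Each rejected in 5.0% to 5.7% of runs; at least one rejected in 14.0%. That figure is the worst case if the most favourable reading were reported.

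**The case against.** The strongest reply is that a time model is implied. The SAP speaks of random slopes over time, compares them with a random-intercept model, calls later variables additional, and places the AIC sentence after the two covariate questions. The natural reading may be a time model first and covariate models second. This has weight, and it is why the consequences above are conditional on the selected model being used for the primary test. It does not close the gap: even if ICU day is always kept, its form, the contrast and the scale remain open.

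It is also fair that the aim is descriptive, and that Appendix 1 ties measurement accuracy to FiO2, PEEP and renal replacement therapy, so adjusting for them is defensible. That is a choice of estimand, and the SAP should make it openly. The results in Step 2 follow from the assumed inputs and do not predict the size here.

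A reader might infer more than the documents support:

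- *That nothing is prespecified.* Model class and random intercepts are, and the protocol fixes unit and population.
- *That ICU day could be dropped by selection.* The text does not exclude this, but does not say it either.
- *That ICU day sits only among same-day covariates.* The list also holds age, sex, body weight and diagnostic group.
- *That keeping PEEP or FiO2 means a complete-case loss of non-ventilated measurements.* These variables are collected under the condition "If YES to invasive mechanical ventilation", so they are structurally absent otherwise. But the SAP drops observations only when missingness is below 3% at each time point and missing at random can be assumed, so it does not prescribe that loss.
- *That the random-slope rule ("Random slopes over time will be included in the model if their respective estimated coefficients are statistically significant", and AIC improves) inflates error.* In 1400 null runs at each of four slope SDs (0, 1, 2 and 3 kcal/kg per 10 days), the rule gave 4.6, 4.6, 6.1 and 6.1%, against 4.5, 4.5, 6.1 and 6.1% with a prespecified slope. There is no case against it here.
- *That 14.0% is the error rate of the AIC procedure.* It is not.

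**Conclusion.** The concern holds in a limited form and should be fixed. The SAP does not name the time term or contrast tested at 0.05, and that rests on the text alone. If the AIC-selected model supplies the primary result, its day effect is a different estimand from the mean change in the Hypothesis section, with post-selection inference. Whether that effect would be smaller, larger or the same cannot be known from the documents. The range of 0.50 to 1.49 against 1.0 only illustrates assumed covariate shares between 50% and -50%. Inflation from selection is a secondary matter, clear at strong drift only. Drop-out and the SAP's censoring weights were not simulated.

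**What to change.** Before analysis, add one paragraph to the SAP that names a single primary model:

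- Outcome: REE in kcal/kg adjusted body weight/24 h. Population: ICU stay over 10 days.
- Time forced in, protected from selection, in one fixed form; for example the three protocol phases with a 2-df joint test at 0.05.
- Reporting scale, difference or ratio, fixed in advance.
- Random intercepts for patient and site and the censoring weights kept as planned. The random-slope rule may stay.
- No data-driven covariates; at most baseline covariates fixed in advance.

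Report adjustment for measurement conditions (FiO2, PEEP, renal replacement therapy) as a prespecified sensitivity analysis. State that PEEP and FiO2 do not exist for non-ventilated measurements and how those measurements are handled. Keep the AIC-selected models as exploratory answers to the SAP's two covariate questions, with their intervals labelled post-selection.

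The cost is SAP wording and one simpler model, with no new data. The downside is that some change in measurement conditions may remain in the primary time effect; the sensitivity analysis is there to show how much. The documents do not say whether the database is already locked. If it is, the paragraph should be dated and described as written after lock.

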Frequencies and patterns of missing data will be investigated for each outcome and explanatory variable by studying summary tables and plots. If missing at random can be assumed and frequencies are below 3% at each time point, this missingness will be ignored, and observations dropped. Explanatory variables with more than 30% missing values at baseline will not be considered, except for the SOFA score, which is not available in the Australian subpopulation. SOFA score will be investigated in non-Australian patients only. As an exploratory analysis, the SOFA score will be imputed in the Australian cohort. Multiple imputation will also be investigated for explanatory variables between 3 and 30% missing values at baseline. If missing at random cannot be assumed, alternative modelling approaches will be considered. Conditional logistic regression will be used to calculate the inverse probability of censoring weights to control for selective drop-out in patients discharged alive from the ICU.

For hypothesis-generating purposes, longitudinal K-means clustering or clustering with dynamic time warping will be used to investigate potential subpopulation phenotypes based on transitions in energy expenditure over time, as appropriate.

All analyses will be performed in R version 4.4.0 or later. The predetermined level of statistical significance for the primary outcome is set to  $\leq 0.05$ . For all other outcomes, no adjustments for multiple comparisons will be made due to the explorative nature of this part of the study. Hypotheses will be generated for target populations with similar characteristics as our sample population, leaving external validity investigations to future confirmatory studies.

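### Covariate 95% confidence intervals come from a model chosen by stepwise selection and AIC but are reported as if it had been fixed in advance; unless the listed variables are forced in, they do not have 95% coverage

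*Combined protocol and SAP*

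**What the plan says.** The section headed Statistical analysis plan (updated 2025-04-08) fits mixed models for four outcomes: REE, RQ, VO2 and VCO2. It introduces the covariates thus: "Explanatory variables will include a group of potentially relevant variables". By my count 13 items follow, about 14 coefficients if diagnostic group is one medical/surgical term plus sepsis yes/no. The next sentence reads: "Further variable selection will be conducted in a data-driven way, either backward or forward selection, as appropriate". No direction or threshold for entry or removal is fixed.

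Two uses of the models are named: "First, we want to explore possible associations with each outcome variable", and "Second, we want to study how well the explanatory variables taken together explain the variation in each outcome variable". On choice of model and reporting, the section says: "The best final adjusted models will be selected based on the AIC. Results will be reported as (exponentiated) regression coefficients and 95% confidence intervals".

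Neither the SAP nor the protocol's Statistics section mentions a post-selection interval, a bootstrap of the selection, shrinkage, cross-validation or a report of the full model.

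**The concern.** An ordinary 95% interval has its stated coverage when the covariate set is fixed before the data are seen. Here a term reaches the results table only if its estimate was large enough to pass AIC. Weak or null terms that pass are those whose estimates fell far from zero by chance, and their intervals are centred on those estimates.

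At stake are the error bars on the covariate findings. The Aim section places the clinical characteristics that go with energy expenditure inside the overall aim, so these results are more than an aside. A reader sees only the terms that were kept, so coverage among kept terms is the relevant quantity.

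**Working it through.** **Inputs from the documents.** AIC as final criterion; 95% intervals; 13 listed items; four outcomes (SAP). At least 200 patients staying more than 10 days and about 1250 patients in all (Sample size considerations).

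**Inputs not in the documents.** Effect sizes, standard deviations, covariate correlations and measurements per patient. Wherever these enter below, they are assumptions.

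**Step 1: the plan's own figure.** The nominal level is 95%, and 2 × (1 − Φ(1.96)) = 0.05. In simulations of a fixed model with 14 covariates (a linear approximation to the mixed model, 200 or 1250 independent units, covariate correlation 0, 0.3 or 0.5), ordinary intervals for null covariates covered 94.2-95.4%. The label is correct when nothing is selected.

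**Step 2: a null term under AIC.** AIC keeps a one-parameter term when its chi-square exceeds 2, that is when |z| > √2 = 1.41.
- P(kept) = P(|Z| > 1.41) = 0.157.
- P(interval excludes zero, given kept) = 0.05 / 0.157 = 0.318.
- Coverage given kept = 1 − 0.318 = 0.682, or 68%.

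These figures need only the AIC rule and normal theory. In the Step 1 simulations, backward and forward AIC gave 61-69%. If the stepwise part used p < 0.05, coverage of kept nulls would be 0%, because every kept null then has an interval excluding zero.

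**Step 3: terms that are not null.** With true effect d in standard-error units, coverage given kept is P(|Z − d| < 1.96 and |Z| > 1.41) / P(|Z| > 1.41), where Z is normal with mean d and SD 1.
- d = 0.5: 0.158 / 0.208 = 76%.
- d = 1: 0.314 / 0.347 = 91%.

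In the simulations, kept non-null covariates covered 94-95% under AIC, and a time term forced into the model covered 93-95%.

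**Step 4: pooled over the reported table.** The answer depends on the mix of null and real terms. By hand, take 14 candidates, 9 of them null, with the 5 real ones strong enough always to be kept and to cover 95%. Nulls kept: 9 × 0.157 = 1.41. Pooled coverage = (1.41 × 0.682 + 5 × 0.95) / (1.41 + 5) = 5.71 / 6.41 = 89%. Simulations (200 patients × 5 measurements, patient SD 4 and residual SD 2.5 kcal/kg, correlations 0 and 0.3) gave roughly 83-88%. If every candidate were null, Step 2 gives about 68%; if every one were strong, about 95%.

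**Step 5: false associations.** Per null candidate, counting those dropped, the rate under AIC is 0.157 × 0.318 = 0.05, the same as without selection. Simulated false associations per model with 9 nulls were 0.45 with selection against 0.42 without (uncorrelated), and 0.64 against 0.46 (correlation 0.3). The Step 1 simulations gave 4.7-6.5% per null with AIC against 4.6-5.8% in the full model.

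**Step 6: explained variation.** Apparent minus true R² in the Step 1 simulations:

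| Units | After AIC | Full model |
|---|---|---|
| 200 | 0.05-0.09 | 0.06-0.11 |
| 1250 | 0.010-0.015 | 0.012-0.018 |

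**Step 7: is selection needed?** With about 14 coefficients there are 200 / 14 ≈ 14 patients per coefficient in the long-stay group and 1250 / 14 ≈ 89 overall. Sample size does not force a reduction.

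**The case against.** The best defence is that the SAP calls everything beyond the primary outcome explorative, makes no multiplicity adjustment there and leaves external validity to later studies. That tempers how the findings may be read. It does not turn a 68% interval into a 95% one, and the label is used to justify the lack of multiplicity adjustment, not the selection.

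A second defence is textual. The listed variables may be meant to stay, with selection applied only to extra ones. The wording permits this, and the problem would then be confined to the extras. But the SAP does not say that the listed variables are forced in, and the sentence "The best final adjusted models will be selected based on the AIC" covers the adjusted models generally.

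A third stands in part: a single model holding every listed variable would not work as it is. Data collection records PEEP and FiO2 only under invasive ventilation, and the SAP sets aside covariates with more than 30% missing at baseline. The fix allows for both.

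A reader might also infer more than the documents support:
- **That selection floods the results with false associations.** Step 5 shows little rise. Most of that burden comes from testing many candidates on four outcomes: if all 13 were null, 13 × 0.05 × 4 = 2.6 would be expected with no selection at all.
- **That selection inflates explained variation.** Step 6 shows slightly more optimism in the full model. The cause is overfitting, so removing selection alone would not cure it.
- **That AIC values will be compared across different rows**, because the SAP says of data missing at random that if "frequencies are below 3% at each time point, this missingness will be ignored, and observations dropped". It does not say that rows are dropped separately for each candidate model; one common complete-case set fits the wording equally well.

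**Conclusion.** The point holds for the covariate intervals. As written, they are ordinary intervals from a selected model, and unless the listed variables are all forced in they do not have 95% coverage. For a null one-parameter term that survives AIC, coverage is about 68%, which rests only on the AIC rule. Pooled over reported covariates it is roughly 83-88% under the assumed effect sizes, variances and correlations, and other mixes of null and real effects would move it.

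Terms with strong true effects lose little. It would be wrong to conclude that the primary time result is undermined: a time term that is always kept covered 93-95%. The SAP should nevertheless say that days in ICU is always kept, which it does not do now.

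This should be changed before analysis. It affects the reporting of associations rather than the validity of the study.

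**What to change.** Replace the selection sentence with one pre-specified model per outcome. It holds days in ICU, forced in, and all listed covariates that meet the SAP's own missingness rule. Take the main coefficients and 95% intervals from this model.

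Because PEEP and FiO2 exist only for ventilated measurements, enter them through a ventilation indicator with interaction, or in a separate model restricted to ventilated measurements.

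Report explained variation with an optimism correction, by a bootstrap that resamples patients or by cross-validation.

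If an AIC-reduced model is still wanted, show it as secondary and fit all candidates on one common set of rows. Either give bootstrap intervals that repeat the whole selection, or state plainly that its intervals are not adjusted for selection.

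The cost is SAP wording and a bootstrap run, with no new data. Some intervals will be slightly wider, and the explained-variation figure will look less favourable.

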- Sepsis during ICU stay (YES/NO, if yes → septic shock or sepsis)

On completion of enrollment at an individual study site:

- Total number of patients admitted during the study period.

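### The planned sepsis sensitivity analysis cannot separate the effect of the sepsis definition from the effect of the Australian cohort, because no fit with primary diagnosis alone is specified

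*Combined protocol and SAP*

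**What the plan says.** The SAP (updated 2025-04-08) lists sepsis among the explanatory variables, within "diagnostic group (medical, surgical, presence/absence of sepsis". Footnote 1 defines it: "Classified as Sepsis-3 och primary diagnosis of sepsis. Sepsis-3 coding is not available in the Australian cohort". The footnote then gives the only check on that definition: "A sensitivity analysis including or excluding the primary diagnosis of sepsis will be performed".

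The purpose of the explanatory variables is stated in the same section: "First, we want to explore possible associations with each outcome variable". The covariate set is not fixed: "Further variable selection will be conducted in a data-driven way, either backward or forward selection, as appropriate".

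For SOFA, the other item absent in Australia, the missing-data paragraph gives an explicit rule: "SOFA score will be investigated in non-Australian patients only". There is no such rule for sepsis.

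The protocol's Data collection section has two items that could feed the sepsis variable: on admission, "Admission diagnosis (ICD-10"), and on discharge, "Sepsis during ICU stay (YES/NO, if yes", with a split into sepsis and septic shock). The footnote does not say which item supplies which criterion.

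**The concern.** The sepsis label differs by cohort. Outside Australia it can use two criteria; in Australia only the primary diagnosis is left. The sensitivity analysis should therefore show how much the sepsis coefficient depends on having primary diagnosis in place of Sepsis-3. Only non-Australian patients have both criteria, so only they can show this directly.

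The planned check varies something else. It adds or removes the primary diagnosis, and removing it takes away Australia's only label. A small difference between the runs could be read as reassurance that the definition does not matter. A large one could be put down to the definition when it reflects a different sepsis association in Australian patients. If the data-driven selection is rerun for each fit, a change of covariates is a third possible source. What is at stake is the reported association of sepsis with REE, RQ, VO2 and VCO2.

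**Working it through.** The plan gives no figure for this check, so there is nothing to reproduce. I set out what each reading delivers and then use illustrative arithmetic.

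**1. What each run contains**

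| Joining word | Run including primary diagnosis | Run excluding it |
|---|---|---|
| 'or' | Outside Australia: either criterion. Australia: primary diagnosis only | Outside: Sepsis-3. Australia: no usable label |
| 'and' | Outside: both criteria. Australia: nobody can be septic | Outside: Sepsis-3. Australia: no usable label |

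'Och' is Swedish for 'and', but only 'or' gives Australian patients a working label, so 'or' is the natural reading. No cell has primary diagnosis alone outside Australia. The footnote does not say what happens to Australian patients in the second run. In a small mixed-model simulation (1250 patients, 10 sites of which 3 Australian, 60 runs, some convergence warnings), dropping them or coding them all non-septic gave almost the same sepsis coefficient, 1.01 and 1.00 against a true 1.

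**2. Label and cohort are confounded ('or' reading)**

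All inputs are assumed: Sepsis-3 effect 1, Sepsis-3 prevalence 0.4, Australian share 0.30. The cohort-adjusted coefficient is

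sum of share × cov(label, Sepsis-3) / sum of share × var(label).

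Scenario A, poor label and equal effects (primary diagnosis has sensitivity 0.4 and specificity 0.98 for Sepsis-3):
- Outside Australia, P(label) = 0.4 + 0.6 × 0.02 = 0.412; cov = 0.4 × 0.588 = 0.2352; var = 0.412 × 0.588 = 0.2423.
- Australia, P(label) = 0.4 × 0.4 + 0.6 × 0.02 = 0.172; cov = 0.16 - 0.4 × 0.172 = 0.0912; var = 0.172 × 0.828 = 0.1424.
- All sites: (0.7 × 0.2352 + 0.3 × 0.0912) / (0.7 × 0.2423 + 0.3 × 0.1424) = 0.1920 / 0.2123 = 0.904. Sepsis-3 alone gives 1.000. Gap -0.096.

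Scenario B, perfect label and an Australian effect of 0.681: 0.7 × 1 + 0.3 × 0.681 = 0.904. Gap -0.096 again.

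Primary diagnosis alone tells them apart. In A it gives 0.0912 / 0.1424 = 0.64 both inside and outside Australia. In B it gives 1.00 outside and 0.681 inside.

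**3. How much of the gap is Australian**

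The rest of the gap comes from non-Australian patients with a primary diagnosis but no Sepsis-3. Take shares of 10-50%, prevalence 30-50%, sensitivity 0.3-0.9 and specificity 0.98.
- Lowest (10%, 30%, 0.9): total gap 0.0490, non-Australian part 0.0446; (0.0490 - 0.0446) / 0.0490 = 9%.
- Highest (50%, 50%, 0.3): total gap 0.1803, non-Australian part 0.0196; (0.1803 - 0.0196) / 0.1803 = 89%.

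**4. How much of the Australian label loss the gap shows**

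In scenario A the loss is 1 - 0.64 = 0.36 and the gap is 0.096, so the planned comparison shows 0.096 / 0.36 = 27% of it. Over 27 combinations (share 10/30/50%, prevalence 30/40/50%, sensitivity 0.3/0.6/0.9) the fraction is 10-39%, 14-54% and 25-74% at the three sensitivities. It is below 100% in all of them.

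**5. Precision of a same-patient comparison**

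This used 1500 simulated studies of 1250 patients (the protocol's planning figure). Assumed inputs: 30% Australian; 30% septic at admission, 80% of these captured by primary diagnosis; 20% of the rest acquiring sepsis later; effect 2 kcal/kg/24 h; patient SD 4, residual SD 2.5; log-normal stay with median 6 days and log-SD 0.8, limited to 2-60 days; measurements from day 2 every 3.5 days. Root mean square error (RMSE) is the square root of (bias² + SD²).

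| Sepsis effect | True change | Planned difference (SD), RMSE | Same-patient difference (SD), RMSE |
|---|---|---|---|
| Constant over the stay | 2 × (0.721 - 1.000) = -0.558 | -0.133 (0.149), 0.45 | -0.540 (0.286), 0.29 |
| Only from onset | 2 × (0.808 - 0.836) = -0.056 | -0.021 (0.149), 0.15 | -0.059 (0.289), 0.29 |

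**The case against.** The strongest reply is that one ambiguous sentence is being made to carry too much, and several parts of that stand.

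- **Loss of Australian patients is inferred.** The missing-data paragraph could lead elsewhere: multiple imputation is to be investigated at 3-30% missing at baseline, and above 30% a variable is not considered, SOFA excepted. This stands as a reason to state the rule. It does not rescue the check, since neither route supplies observed Australian Sepsis-3 data.
- **The literal 'and' reading comes close to the missing fit.** If nearly every primary-diagnosis case also meets Sepsis-3, the 'and' label outside Australia is almost primary diagnosis alone. That is correct, but the main definition then classes no Australian patient as septic.
- **A reader might infer that the check is mainly a comparison with and without Australian patients.** The documents do not support 'mainly': the Australian part runs from 9% to 89% on undocumented inputs.
- **A reader might also infer that Australia's label loses about a quarter of the association.** That rests on taking Sepsis-3 as a whole-stay item and primary diagnosis as an admission item, which the SAP does not state. With step 5's inputs, patients without a primary diagnosis make up 1 - 0.3 × 0.8 = 0.76 of the total. Septic patients among them are 0.06 + 0.7 × 0.2 = 0.20, a loss of 0.20 / 0.76 = 26%. Without acquired sepsis it is 0.06 / 0.76 = 8%.
- **The same-patient comparison is not always more accurate.** This stands: it has the lower error when the effect is constant over the stay and the higher error when the effect starts at onset.
- **Materiality is modest.** Sepsis is one candidate covariate, and the SAP calls everything beyond the primary outcome explorative. This stands and limits the weight of the point.

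**Conclusion.** The point holds in a limited form. Under 'or', the planned comparison confounds the definition with the loss of Australian sepsis information; under 'and', Australia has no septic patients. Under neither does the SAP specify a fit on primary diagnosis alone, so the check cannot separate label from cohort. This follows from the text and needs no assumed input.

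The size is not known. It depends on the Australian share, the agreement between the criteria and the source fields, none of which the documents give. The simulated and algebraic figures show that the confounding is possible and that the gap can understate a label effect; they do not measure a defect in this study. Nor do the documents support extending the concern to the primary result: sepsis is an adjustment variable there, and the time effect on REE is not materially affected. This is a worthwhile improvement to an exploratory analysis.

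**What to change.** Keep the main definition and amend footnote 1 as follows.

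1. Replace 'och' with the intended word and name the data field behind each criterion. If the discharge item is used, describe the variable as sepsis at any time during the ICU stay.
2. State that the run excluding the primary diagnosis is limited to non-Australian patients, as is already done for SOFA.
3. In those same patients, with one fixed covariate set, fit three labels: Sepsis-3 alone, primary diagnosis alone, and the composite. Read the label effect from these fits.
4. Fit primary diagnosis alone across all sites, or inside versus outside Australia, as the harmonised-label check. Read the cohort difference from this.
5. Report the cross-table of the two criteria in non-Australian patients.

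The cost is SAP wording, one table and a few extra fits per outcome. No new data are needed, provided the primary diagnosis comes from the ICD-10 admission field. The drawback is precision: the same-patient difference has a simulated SD of about 0.29 kcal/kg/24 h at 1250 patients under the assumed inputs. It should be read with its confidence interval and the cross-table. Step 4 also assumes that primary-diagnosis coding captures sepsis similarly in both cohorts, which should be stated as a limitation.
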